### **8.2.8 Statistical Methods for Safety Analyses**

Subjects from all three arms (40 mg / 40 mg, 12 mg / 12 mg, Pbo / 40 mg) will be included in the safety analyses. Where applicable, treatment comparisons will be conducted between the 40 mg / 40 mg and Pbo / 40 mg arms, as well as between the 12 mg / 12 mg and Pbo / 40 mg arms.

Safety and tolerability will be assessed by clinical review of all relevant parameters including AEs, laboratory tests, vital signs, and ECG measurements. The primary approach for all safety analyses will be an On Drug approach, i.e., one that includes only those observations obtained from the first dose through 14 days after the last dose of study medication. A supportive approach will include all post-treatment observations, including those observations obtained more than 14 days after the last dose of study medication.

The analysis of safety results will follow a tiered approach (Table 7). The tiers differ with respect to the analyses that will be performed. Safety parameters or adverse experiences of special interest that are identified a priori constitute “Tier 1” safety endpoints that will be subject to inferential testing for statistical significance with p-values and 95% confidence intervals provided for between-group comparisons. Other safety parameters will be

considered Tier 2 or Tier 3. Tier 2 parameters will be assessed via point estimates with 95% confidence intervals provided for between-group comparisons; only point estimates by treatment group are provided for Tier 3 safety parameters.

Adverse experiences (specific terms as well as system organ class terms) and predefined limits of change in laboratory, vital signs, and ECG parameters (see Section 12.3) that are not pre-specified as Tier-1 endpoints will be classified as belonging to "Tier 2" or "Tier 3", based on the number of events observed. Membership in Tier 2 requires that at least 1% of the subjects in any treatment group exhibit the event; all other adverse experiences and predefined limits of change will belong to Tier 3.

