The threshold of "at least 1%" was chosen because the expected number of subjects in the ASaT population is expected to be greater than 400 per treatment group. Thus an incidence of at least 1% in a treatment group translates to at least four subjects experiencing that event in the treatment group, which is the minimum number needed to attain statistical significance at  $\alpha=0.05$ . Because many 95% CIs may be provided without adjustment for multiplicity, the CIs should be regarded as a helpful descriptive measure to be used in review, not a formal method for assessing the statistical significance of the between-group differences in AEs and PDLCs.

Continuous measures such as changes from baseline in laboratory, vital signs, and ECG parameters that are not pre-specified as Tier-1 endpoints will be considered Tier 3 safety parameters. Summary statistics for baseline, on-treatment, and change from baseline values will be provided by treatment group in table format.

For this protocol, 1) microhemorrhage, superficial siderosis or macrohemorrhage; 2) vasogenic edema; 3) delirium; and 4) rash ECI (see Section 7.2.3.2 for definition) are considered as Tier 1 events. The broad clinical and laboratory AE categories consisting of the percentage of subjects with any AE, a drug related AE, a serious AE, an AE which is both drug-related and serious, and who discontinued due to an AE will be considered Tier 2 endpoints. A composite endpoint of hypopigmentation adverse events is defined based on the following preferred AE terms or equivalent: (noting that MedDRA terms are subject to change over time): skin hypopigmentation, skin depigmentation, vitiligo, leukoderma, hypopigmentation of eyelid, and idiopathic guttate hypomelanosis. This composite AE of hypopigmentation will be considered as either a Tier 2 or Tier 3 AE, per the criteria for Tier 2 AEs defined above. P-values (Tier 1 only) and 95% confidence intervals (Tier 1 and Tier 2) will be provided for between-treatment differences in the percentage of subjects with events; these analyses will be performed using the Miettinen and Nurminen method [27], an unconditional, asymptotic method.

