The prespecified categories of suicidal ideation and behavior will be analyzed per the tiered analysis strategy outlined above, and will be considered as either Tier 2 or Tier 3 AEs, depending on the percent of events observed within each treatment group. Counts for each category will be based upon events observed during the assessment period (without consideration of prior history).

Safety analyses will only be based on subjects who treated in the long term trial. Unless otherwise noted, postdose data from the initial 104-week trial will not be analyzed with data from the long term trial.

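### Section 8.2.8 sizes the safety population at over 400 per group although its own restriction to extension-treated subjects implies about 304, and its extension-only Tier 1 p-values lack a descriptive label and a display by time since first dose

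*Combined protocol and SAP*

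**What the plan says.** Section 8.2.8 states: "Safety analyses will only be based on subjects who treated in the long term trial". It continues: "Unless otherwise noted, postdose data from the initial 104-week trial will not be analyzed with data from the long term trial". No exception for safety is noted anywhere in the document.

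On size, the same section justifies its 1% Tier 2 threshold on the ground that "the expected number of subjects in the ASaT population is expected to be greater than 400 per treatment group", so that 1% means at least four subjects, given as the fewest that can reach significance at 0.05. Section 8.2.5 defines ASaT as everyone randomized and dosed and does not mention the extension.

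On comparisons, "treatment comparisons will be conducted between the 40 mg / 40 mg and Pbo / 40 mg arms"; Pbo/40 is also the comparator for 12/12. Tier 1 events "will be subject to inferential testing for statistical significance with p-values and 95% confidence intervals provided for between-group comparisons", and Table 7 assigns a p-value to each. The caveat in 8.2.8 covers intervals only: "the CIs should be regarded as a helpful descriptive measure to be used in review". The primary On Drug approach "includes only those observations obtained from the first dose through 14 days after the last dose of study medication", without saying which trial's first dose is meant.

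**The concern.** Two things do not fit together.

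First, a population limited to extension entrants cannot have the size expected of the whole randomized trial. The figure over 400 is the stated reason for the 1% rule, and a programmer who follows 8.2.5 literally would build a different denominator from one who follows the end of 8.2.8.

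Second, former placebo subjects all start 40 mg in the extension (section 5.2). Subjects in 40/40 and 12/12 must as a rule have tolerated and completed 104 weeks (5.1.2, with Sponsor-discretion exceptions there and in 4.2.1.2). With initial-trial data left out, a Tier 1 comparison sets first exposure beside later exposure in subjects selected for tolerance; 12/12 v Pbo/40 also mixes in dose. An early-onset event would tend to favour the longer-exposed arm and a late-accumulating one the reverse, and the Tier 1 table alone does not show which applies. Safety is the first primary objective (3.1), and 4.2.2.3 names rash, a Tier 1 event, as a possible risk.

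**Working it through.** **Inputs.** 450 randomized per arm (1350 in total) and 25% dropout at Week 104 (Table 9); 90% of completers continuing (8.2.11.1.2); about 912 extension subjects (1.0). The 37% dropout at Week 130 is not used, because a safety population counts everyone dosed.

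**Reproducing the enrolment figure.** 1350 × 0.75 × 0.90 = 911.25, which agrees with about 912.

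**Per-arm safety size.**
- Plan's assumptions: 450 × 0.75 × 0.90 = 303.75; also 912 / 3 = 304.
- Every completer continues: 450 × 0.75 = 337.5.
- To exceed 400: 401 / 450 = 89.1% of randomized subjects would have to enter, which 25% dropout rules out.
- All randomized and dosed: up to 450. Only this reading fits the stated figure.

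**The 1% rule.** The Miettinen-Nurminen statistic at zero difference is z = (p1 − p2) / √[p̄(1 − p̄)(1/n1 + 1/n2) × N/(N − 1)], with N = n1 + n2.
- n = 400: 1% is 4 subjects; 4 v 0 gives p = 0.045. The plan's four-subject minimum reproduces.
- n = 304: 1% is 3.04, so four subjects are still needed (3/304 = 0.99%, 4/304 = 1.32%); 4 v 0 gives z = 2.00, p = 0.045.
- n = 300: three subjects reach 1%; 3 v 0 gives z = 1.73, p = 0.083.
- The margin is thin: 300 / 337.5 = 88.9%, so continuation at or below that, against the assumed 90%, brings an arm to 300 or fewer.

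**Exposure timing.** The contrast follows from the sections cited above and needs no assumed rates. Section 8.2.15 tabulates doses taken by timeframe, but no section tabulates adverse events by time since first MK-8931 dose. The efficacy analyses do use both periods (8.2.7.1, 8.2.7.2).

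**Illustration only.** The rates below are assumptions, because the documents give none. Entries are the chance of two-sided p < 0.05 at 304 per arm, by binomial enumeration.

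| 40/40 | Pbo/40 | Chance of p < 0.05 |
|---|---|---|
| 1% | 1% | 2.3% each way |
| 1% | 3% | 43%, favouring 40/40 |
| 1% | 5% | 87%, favouring 40/40 |
| 4% | 1% | 70%, favouring Pbo/40 |

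The effect fades with follow-up. Suppose the risk by time since first dose is the same in both arms: 3% in the first 26 weeks, then 1% per 26 weeks, with no dropout. With k = weeks/26, cumulative risk is 1 − 0.99^k in 40/40 and 1 − 0.97 × 0.99^(k−1) in Pbo/40. At 26, 52 and 104 weeks this gives 1.00 v 3.00%, 1.99 v 3.97% and 3.94 v 5.88%, and chances of 43%, 30% and 20%.

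**The case against.** The contrast is open. Section 3.1 names it for both primary objectives, 4.2.1.1 describes a delayed-start design, and the arm labels show who starts when. Sections 8.1.1 and 8.2.10 disclaim formal hypotheses. Safety is judged by clinical review with an external monitoring committee, and nothing in the document ties a decision to a Tier 1 p-value. The placebo-controlled question belongs to the initial trial, which is described in a separate amendment; an integrated analysis may be planned there or elsewhere. A display by time since first dose would not be randomized. On size, the closing paragraph of 8.2.8 is the more specific text and largely settles the population and the On Drug window.

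Most of this stands, and it limits the weight of the point. Two parts do not answer it. The descriptive caveat names the intervals and rests on multiplicity, not on exposure timing, so the p-values remain unqualified. And the over-400 figure stays wrong for the population that 8.2.8 itself specifies.

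A reader might infer that the Tier 1 comparisons are invalid, or that they will make longer treatment look safer. The documents do not support either. The comparison is a stated objective, the plan does not claim that it isolates a drug effect, and with no rates or onset times the direction is open.

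**Conclusion.** The stated safety size is wrong as written: about 304 per arm under the plan's assumptions, at most 337.5, against a figure over 400. This is a consistency error with little numerical effect. It would be going too far to say that it upsets the tier rule: at 304 the cut-off is still four subjects, and at 300 or fewer the only result is that some events move from Tier 3 to Tier 2 and gain an interval. The 304 is itself a projection. Section 1.0 says that enrolment may vary, and the documents do not say whether the 90% continuation allows for excluding subjects who progressed to dementia.

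The labelling and the added display are an inexpensive improvement rather than the repair of an invalid analysis. That the extension-only p-values cannot by themselves separate drug effect from exposure timing follows from the design. How much this matters is unknown, and the probabilities in the illustration should carry no weight beyond showing the mechanism.

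**What to change.** **Correct the text.**
1. In 8.2.5, define the safety population for this trial as subjects treated in the extension.
2. In 8.2.8, replace the over-400 figure with about 304 per arm under the plan's assumptions. Restate the 1% rationale at that size, noting that three subjects reach 1% at 300 or fewer.
3. State that the On Drug window for the extension analyses starts at the first extension dose, consistent with the exclusion of initial-trial post-dose data.

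**Improve the presentation.**
4. Label the Tier 1 p-values as descriptive early-start v delayed-start contrasts, and note that 12/12 v Pbo/40 also differs in dose.
5. For delirium and rash ECI, add cumulative incidence and exposure-adjusted rates by time since first MK-8931 dose. Use initial plus extension data for the 12 mg and 40 mg arms, and extension data for Pbo/40. This sets the first 40 mg exposure of about 450 original subjects beside that of about 304 Pbo/40 subjects, and serves the purpose that 4.2.1.2 gives for treating the placebo group with 40 mg.
6. State that this display is not a randomized comparison, since Pbo/40 entrants are mostly completers, without AD dementia at entry, two years on. Check that visit spacing after first dose is similar; the initial-trial schedule is not in this document. Leave out the MRI endpoints unless the move from routine to clinically indicated scanning (4.2.2.2, 7.2.3.2) is accounted for.

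The cost is wording in two sections and a few tables from data already held. No procedure is added and no Tier 1 endpoint changes tier.

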**Table 7 Analysis Strategy for Safety Parameters**

Safety Tier	Safety Endpoint †	p-Value	95% CI for Treatment Comparison	Descriptive Statistics
Tier 1	Incident Microhemorrhage, superficial siderosis or macrohemorrhage in brain MRI scans	X	X	X
	Incident Vasogenic edema	X	X	X
	Delirium	X	X	X
	Rash ECI	X	X	X
Tier 2	Any AE		X	X
	Any Serious AE		X	X
	Any Drug-Related AE		X	X
	Any Serious and Drug-Related AE		X	X
	Discontinuation due to AE		X	X
	Specific AEs, SOCs, or PDLCs ‡ (incidence ≥1% of subjects in one of the treatment groups)		X	X
Tier 3	Specific AEs, SOCs or PDLCs ‡ (incidence <1% of subjects in all of the treatment groups)			X
	Change from Baseline Results (Labs, ECGs, Vital Signs)			X

†Adverse Experience references refer to both Clinical and Laboratory AEs.  
‡Includes only those endpoints not pre-specified as Tier 1 or not already pre-specified as Tier-2 endpoints.  
 Note: SOC=System Organ Class; PDLC=Pre-Defined Limit of Change; X = results will be provided.

## 8.2.9 Summaries of Baseline Characteristics, Demographics, and Other Analyses

### 8.2.9.1 Demographic and Baseline Characteristics

The comparability of the treatment groups for each relevant characteristic will be assessed by the use of tables and/or graphs. No statistical hypothesis tests will be performed on these characteristics. The number and percentage of subjects screened, randomized, the primary reasons for screening failure, and the primary reason for discontinuation will be displayed. Demographic variables baseline characteristics, primary and secondary diagnoses, and prior and concomitant therapies will be summarized by treatment either by descriptive statistics or categorical tables.

### 8.2.10 Multiplicity

In the initial 104-week trial, strong Type I error control is achieved through the utilization of a Bonferroni approach in conjunction with a closed testing sequential approach. Specifically, a separate hypothesis family is created for each of the two active doses, with each hypothesis within a family tested sequentially at the  $\alpha=0.02495$  level.

As there are no formal hypotheses for the long term trial, there is no need for a formal multiplicity strategy. However, 97.51% CIs will be produced for all endpoints with corresponding hypotheses conducted under strong control from the initial 104-week trial, even though formal hypotheses are not defined in this long-term safety trial, and it is acknowledged that strong control is not present.

### 8.2.11 Sample Size and Power Calculations

#### 8.2.11.1 Sample Size and Power for Efficacy Analyses

##### 8.2.11.1.1 Parameter Estimates

Parameter estimates for the primary endpoint were obtained from the Alzheimer's Disease Neuroimaging Initiative (ADNI). Extrapolations out to 30 months (Week 130) were performed on the 24-month (Week 104) parameter assumptions used in the initial 104-week trial and these extrapolations are presented below in [Table 8](#).

Table 8 Parameter Assumptions for CDR-SB

Endpoint	Baseline SD	30m SD	30m CFB Mean (130-Week Placebo/ MK-8931 40 mg Progression Rate)	Corr(Base, 30m)
CDR-SB	0.86	3.05	2.13	0.359

Based on N=151 subjects from ADNI, Late MCIs with either CSF+ ( $\tau\text{au}/\text{ab142} \geq 0.39$ ) or PET+ ( $\text{pib} > 1.6$ ), and MMSE  $\geq 24$ .

### 8.2.11.1.2 Power Calculations

Power calculations for the change-from-baseline treatment difference at 30 months (Week 130) were performed (via simulation) for CDR-SB even though there are no formal hypotheses for the endpoint in the long term trial. As shown in Table 9 the hypothesis is underpowered at Week 130, both marginally and when applying an informal sequential testing approach. Specifically, it is possible that formal statistical significance may be observed in the initial 104 week trial (under the prespecified multiplicity approach), while nominal marginal significance (ie, p-value < 0.02495) fails to be observed at Week 130, even if the true underlying effect of MK-8931 continues to increase. This is due to the assumed increased variance and dropout rate over time, with 90% of subjects who complete the base study assumed to continue on into the extension.

Table 9 Power Calculations (MK-8931 40 mg / MK-8931 40 mg vs. Placebo / MK-8931 40 mg)

Marginal Probability †	(%)
CDR-SB at Week 130	73.9
Sequential Probability	
Success ‡ for CDR-SB at Week 104 and CDR-SB at Week 130	73.4
Conditional Probability	
Success ‡ for CDR-SB at Week 130 given success on CDR-SB at Week 104	76.1
† Marginal power calculations at Week 130 do not require success at Week 104. ‡ 40 mg dose only Calculations are based on N=1350 randomized (450 subjects/arm) incorporating the assumed dropout rate of 25% at Week 104 and 37% at Week 130 ( $\alpha = 0.02495$ ).	

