**SUMMARY OF CHANGES**

**PRIMARY REASON(S) FOR THIS AMENDMENT:**

Section Number (s)	Section Title(s)	Description of Change (s)	Rationale
1.0 2.1 4.2.1.2 5.1.3 7.1.2.3.1	Trial Summary  Trial Design  Rationale for Trial and Selected Subject Population  Subject Exclusion Criteria  Confirmation of Progression to Probable AD Dementia	Eligibility criteria modified to exclude subjects who progress to dementia due to AD based on investigator diagnosis in the main 104 week study from entering the long term extension study.	Results of the Phase 2/3 clinical study MK-8931-017 did not show a benefit in AD patients who initiated MK-8931 treatment in the mild to moderate dementia stage. Therefore, the balance of benefit/risk no longer supports entry of subjects with AD dementia in the extension, where active treatment may be newly initiated. Regarding continued treatment of subjects who progress to dementia later in the trial, it is not known whether initiation of treatment at the prodromal stage would provide benefit to these subjects. Therefore, despite the lack of efficacy in the 017 population of subjects with mild to moderate dementia, the sponsor believes that continued treatment of these subjects is warranted.

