## 1.0 TRIAL SUMMARY

Abbreviated Title	A Long Term Safety and Efficacy Trial of MK-8931 (SCH 900931) in Subjects with Prodromal AD (APECS)
Trial Phase	III
Clinical Indication	Treatment of early (prodromal) AD
Trial Type	Interventional
Type of control	Not Applicable
Route of administration	Oral
Trial Blinding	Double-blind
Treatment Groups	MK-8931 12 mg MK-8931 40 mg
Number of trial subjects	All subjects who complete the initial 104 week trial and are willing and qualified to participate in the long term trial will be enrolled. Subjects who progress to dementia due to AD in the main 104 week study will not be permitted to move into the long term extension study. The actual number enrolled may vary depending on the number enrolled in the 104 week trial, the dropout rate, and the number of eligible subjects who consent to enroll. Based on the current sample size projection and estimated dropout rate (25%) for the initial 104 week trial, approximately 912 subjects would be enrolled. The total number of subjects enrolled in the extension will not exceed the total enrolled in the initial 104 week trial.
Estimated duration of trial	The duration of the long-term trial is expected to be up to approximately five years or until a) MK-8931 becomes commercially available (locally), or b) when the MK-8931 program is terminated (whichever comes first). Duration of the trial may be limited based on local regulation.
Duration of Participation	Expected maximum duration of no longer than 260 weeks (5 years after the first subject enrolls), with the duration of individual subject participation dependent on the timing of enrollment. Duration of participation may be limited based on local regulations. Subjects who do not complete the initial 104-week trial of MK-8931 protocol 019 will not be permitted to continue in this trial. In addition, subjects who are less than 75% compliant with trial medication during the initial 104-week trial will require Sponsor approval to participate in this trial. Subjects will be followed for at least 14 days following cessation of treatment.
Randomization Ratio	Not applicable to this trial.

A list of abbreviations used in this document can be found in Section 12.4.

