#### **4.2.1.2 Rationale for Subject Population and Dose**

The recent results from Protocol 017 indicate that MK-8931 is not effective when treatment is initiated in subjects with mild/moderate AD. The amyloid hypothesis suggests, however, that earlier treatment with a BACE inhibitor (prior to the onset of dementia) could be beneficial even if ineffective at later stages. The initial 104-week trial of Protocol 019 in prodromal AD is still ongoing so the impact of BACE inhibition in this earlier stage of the disease is not yet known. Given this uncertainty along with the 017 results, subjects who tolerated study medication, have not progressed to dementia and completed the initial 104-week trial of Protocol 019 may enroll in this long term trial. However, subjects who have progressed to dementia will be excluded since the 017 results indicate increased adverse events in addition to no efficacy.

Subjects in the initial 104 week trial who progress to dementia during that time have a 2 out of 3 chance of being on active treatment with MK-8931. Based on the view that these subjects could still benefit from MK-8931 since it was initiated before the onset of dementia, one alternative is to allow these subjects into the extension trial. However, since the blind will be maintained in the extension, it is not possible to include these subjects while excluding subjects who were on placebo during the initial 104-week trial. Given the concern that the placebo treated subjects who progress to dementia would not benefit from treatment, the current protocol will exclude all subjects who have progressed to dementia.

Subjects who progress to dementia during this extension trial will be allowed to continue, since it is not known whether initiation of treatment at the prodromal stage would provide benefit to these subjects. Therefore, despite the lack of efficacy in the 017 population where treatment was initiated at the mild to moderate dementia stage, the sponsor believes that continued treatment of these subjects is warranted.

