### **5.1.3 Subject Exclusion Criteria**

The subject must be excluded from participating in the trial if the subject:

1. Has progressed to dementia due to AD per investigator diagnosis in the initial 104-week study.
2. Is in imminent risk of self harm, based on clinical interview or on the Columbia Suicidality Severity Rating Scale (C-SSRS), or of harm to others in the opinion of the investigator. Subjects who report suicidal ideation with intent, with or without a plan (e.g., suicidal ideation item 4 or 5 on the C-SSRS) in the past one (1) month or suicidal behavior in the past six (6) months should be excluded. Such subjects will be permitted to rescreen for entry into this study once in the Investigator's opinion, this risk of harm to self or others is no longer present.

3. Has developed a recent or ongoing, uncontrolled, clinically significant medical or psychiatric condition that precludes participation in this protocol in the judgment of the investigator.
4. Based on results from the EOT Visit (Visit 12) in the initial 104-week trial has results of clinical laboratory tests (complete blood count [CBC], blood chemistries, and urinalysis) that are clinically unacceptable to the investigator. However, it is recognized that lab results will not be available at Visit 12/12B if they occur on the same day. Therefore, such subjects may be enrolled prior to receiving these results; upon their receipt of the lab results, if the PI feels they are clinically unacceptable the subject should be discontinued.
5. Based on the results from the EOT Visit (Visit 12) has results of a physical examination, and vital signs that are clinically unacceptable to the investigator.
6. Has developed a form of dementia that is not Alzheimer's Disease, including but not limited to, dementia due to HIV infection, head trauma, vascular disease, Parkinson's disease, frontotemporal dementia, or Huntington's disease, as determined by the investigator.
7. Anticipates receiving any of the treatments listed in [Table 1](#) during the current trial.

Table 1 Prohibited Medications

Prohibited Medications, Supplements, and Other Substances
Anti-amyloid agents (e.g., tarenflurbil, tramiprosate)
Anti-amyloid antibodies (e.g., solanezumab)
Anti-amyloid vaccine (Subjects who received placebo only in a vaccine trial may participate in this trial.)

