### **8.2.7 Statistical Methods for Efficacy Analyses**

#### **8.2.7.1 Primary Efficacy Analysis**

The primary efficacy endpoint is the change from Baseline (CFB) in CDR-SB score at Week 130. Basic summary statistics (means and standard deviations, as observed), will be calculated.

A delayed start design will be used to support the potential disease modifying effect of MK-8931 by comparing the 40 mg/40 mg arm to the Pbo/40 mg arm. However, due to increased variance and anticipated dropout rate over time, the study is not powered to demonstrate significance on these endpoints, even if significance was demonstrated at 24 months in the initial study.

The 12 mg/12 mg arm will be compared to the Pbo/40 mg arm in a similar fashion.

All available data from the initial 104-week trial will be utilized in the analyses, even that from subjects who do not continue into long term trial. It is possible that the 40 mg dose may be dropped for reasons due to safety, in which case all subjects would receive 12 mg. The primary comparison in this case would be between the 12 mg / 12 mg arm and the Pbo / 12 mg arm (with any subjects receiving 40 mg excluded from the analysis).

A longitudinal ANCOVA model will be used on the change scores, with time treated as a categorical variable so as not to impose any restriction on the trajectory of the means over time. The analysis model includes treatment, time, the time-by-treatment interaction, APOE4 genotype (APOE4 positive, APOE4 negative), gender, geographic region, and the use of acetylcholinesterase inhibitors at screening (Use, Do Not Use) as categorical terms, with age and baseline MMSE score as continuous covariates. The baseline value of the dependent

variable, as well as the baseline-by-time interaction term will also be included. Model-based estimates of the mean change scores and the mean treatment difference on the change scores will be provided, along with the corresponding confidence intervals and p-values for the mean treatment differences. An unstructured covariance matrix will be used to model the correlation among repeated measurements.

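### Do the 912 entrants, the 37% Week-130 loss and the Table 9 power fail because the 90% continuation rate ignores the new AD-dementia exclusion?

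*Combined protocol and SAP*

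**What the plan says.** Section 8.2.11.1.2 assumes 450 randomized subjects per arm (1,350 in all), "incorporating the assumed dropout rate of 25% at Week 104 and 37% at Week 130", "with 90% of subjects who complete the base study assumed to continue on into the extension". Table 9 then gives 73.9% marginal power for CDR-SB at Week 130, 73.4% for success at both Week 104 and Week 130, and 76.1% for Week 130 given success at Week 104.

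Section 1.0 gives the size of the extension: "Based on the current sample size projection and estimated dropout rate (25%) for the initial 104 week trial, approximately 912 subjects would be enrolled". The same entry says the actual number may depend on enrolment in the 104-week trial, "the dropout rate, and the number of eligible subjects who consent to enroll".

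Section 5.1.3 excludes a subject who "Has progressed to dementia due to AD per investigator diagnosis in the initial 104-week study". Section 4.2.1.2 applies this whatever the original arm: "the current protocol will exclude all subjects who have progressed to dementia". The Summary of Changes shows the exclusion as new in this amendment, "Eligibility criteria modified to exclude subjects who progress to dementia due to AD based on investigator diagnosis in the main 104 week study", and lists Sections 1.0, 2.1, 4.2.1.2, 5.1.3 and 7.1.2.3.1 for it. No part of Section 8 is listed.

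**The concern.** An exclusion was added that removes completers at the door of the extension. The entry projection and the power table both depend on the share of completers who enter, and neither is logged as revised. If the 90% was set earlier, to allow for refusal, poor compliance and medical exclusions only, then dementia progression comes on top. In that case 912 and the Table 9 power would be too high and 37% too low.

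A second sign points the same way. The two inputs that Section 1.0 names for 912 do not produce it.

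At stake would be the stated size of the trial, and the reader's sense of how likely a Week-130 miss is after a Week-104 success. Table 9 is there to inform that reading.

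**Working it through.** **Inputs.** From 8.2.11.1.2: 450 per arm; 25% loss at Week 104; 37% loss at Week 130; 90% continuation; alpha 0.02495 (taken as two-sided); power 73.9%, 73.4% and 76.1%. From 1.0: about 912 entrants. Not given anywhere: a dementia progression rate among completers, the Week-130 treatment difference behind Table 9, or the correlation between Week 104 and Week 130.

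**Reproducing the plan's figures**

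- Entrants: 450 x 0.75 x 0.90 = 303.75, rounded up to 304; 3 x 304 = 912. This matches.
- Entrants from the inputs named in Section 1.0 alone: 1,350 x 0.75 = 1,012.5. This does not match, so the 90% is needed.
- Week-130 retention: 1 - 0.37 = 0.63. Retention after entry: 0.63 / (0.75 x 0.90) = 0.933, a later loss of about 6.7%.
- Plausibility of that 6.7%: the base-trial dropout rate continued for 26 weeks gives 0.75^(26/104) = 0.931, so the loss is 1 - 0.75 x 0.90 x 0.931 = 37.2%. Without the 90% it is 1 - 0.75 x 0.931 = 30.2%.

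The three figures therefore agree with one another and share the 90% factor.

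**What a larger loss at entry would do.** Let T be the total share of completers who do not enter, for any reason. Every T above 10% is an assumption. Entrants = 1,012.5 x (1 - T). Week-130 loss = 1 - 0.75 x (1 - T) x 0.933.

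For power, the primary model keeps base-trial data from subjects who do not continue (8.2.7.1), so a count of Week-130 observations alone overstates the damage. A two-visit approximation makes the Week-130 variance proportional to (1 - rho^2)/n2 + rho^2/n1, with n1 = 0.75, n2 = 0.75 x (1 - T) x 0.933, and rho the residual correlation between Weeks 104 and 130.

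Calibration to Table 9:

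- P(success at Week 104) = 73.4 / 76.1 = 96.5%.
- The critical z is 2.242, so the standardized effects are 4.048 at Week 104 and 2.882 at Week 130.
- The joint 73.4% needs a correlation of 0.67 between the test statistics, which corresponds to rho of about 0.70.

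| T | Entrants | Week-130 loss | Power, rho 0.70 | Power, rho 0.6 to 0.9 |
|---|---|---|---|---|
| 10% (as stated) | 912 | 37% | 73.9% | 73.9% (calibrated) |
| 15% | 861 | 40% | 72% | 72-73% |
| 20% | 810 | 44% | 71% | 70-73% |
| 28% (20% on top of the 10%: 1 - 0.9 x 0.8) | 729 | 50% | 68% | 66-71% |

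At T = 20% and rho 0.70, power at Week 130 given success at Week 104 falls from 76.1% to 72.9%. The chance of a miss after an earlier success thus goes from about 24% to about 27%.

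**The case for a change.** The strongest case for acting is that the omission in Section 1.0 needs no assumption about progression. The named basis gives about 1,013 and the stated number is 912. The 10% must also absorb refusal, intolerance, compliance below 75%, suicidality, medical exclusions and sites without local approval, so little may be left for dementia in a population selected for prodromal disease. The sponsor chose to print Table 9, so a reader should be able to tell what its retention input contains. The caveat in Section 1.0 covers the realised number of entrants but does not define the 90%.

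The arithmetic stands, and so does the plan's silence on what the 10% contains. The inference to an error does not:

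- A completer barred for dementia is a completer who does not continue. The sentence in 8.2.11.1.2 names no cause and excludes none.
- That the 90% predates the exclusion is inferred only from the change log's silence. A log need not list text that was reviewed and kept, and the 912 stands in the same Section 1.0 entry as the exclusion.
- The projection is given as approximate and is said to depend on the number of eligible subjects who consent, which already allows for eligibility losses.
- The power losses are conditional on an assumed T and on a correlation back-solved from a 0.5-point gap between two simulated percentages. The value of T at which power falls below 70% moves from about 20% at rho 0.6 to about 35% at rho 0.9, so no single threshold can be quoted.

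**Conclusion.** No change is called for. The 912 and the 37% follow exactly from the plan's own assumptions, and nothing in the documents shows that those figures or the Table 9 probabilities are wrong. What remains is a clerical omission in Section 1.0, which leaves out a factor stated in 8.2.11.1.2, and an assumption not broken down by cause. An analyst recovers the first in one multiplication and would read the second as all-cause.

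Even if total non-continuation were 20%, Week-130 power would be roughly 70-73% instead of 73.9%, and a miss after Week-104 success about 27% instead of 24% (the latter at rho 0.70). These sizes assume two visits only, the same unstated treatment difference as in Table 9, an unchanged 93.3% retention after entry, and Week-130 loss explained by the Week-104 score.

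No sample size, alpha level or stopping rule rests on the figures. Section 8.1.3 says the extension has no sample size calculation and no formal hypotheses, and Section 8.2.7.1 warns that "the study is not powered to demonstrate significance on these endpoints". Modestly lower power would leave that conclusion as it is.
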